13.3 Analysis Sets

Eligibility, Protocol Deviations

Enrolling an ineligible participant is a protocol violation that is reportable to the IRB. If Protocol Deviations are identified, the PI will determine whether the protocol should be modified (to prevent further incidents from occurring) and whether the participant should be withdrawn due to safety or other concerns. Enrollment in another clinical study possibly interfering with the endpoints of the present study will be considered a protocol violation.

Each patient's allocation to the different analysis sets will be identified prior to database lock. Significant deviations from the protocol will lead to the exclusion of a subject from the per-protocol analysis set.

Listings will be prepared to show the characteristics of all subjects for the different analysis sets and a summary will be given on the number of subjects per analysis set. A detailed description of the criteria used for data sort out will be provided before start of the evaluations.

Definitions

The statistical evaluation will be based on separate, hierarchically organized analysis sets as defined below:

- Intention to Treat (ITT) analysis set: The safety analysis set will consist of all patients enrolled.
- Safety analysis set: The full analysis set will consist of all patients who received the injection of the IMP.
- Per-protocol analysis set: The per-protocol analysis set will consist of all patients of the ITT analysis set for whom no major protocol violations have been recorded.

Demographic and baseline characteristics will be analyzed for all three analysis sets. General safety data will be evaluated using the safety analysis set. Efficacy parameters will be evaluated using the full analysis set, the per-protocol analysis set, and based on dose of IMP received.

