8.7 Early Termination and Withdrawal

Subjects are free to withdraw from participation in the study at any time upon request.

The Principal Investigator (PI) may discontinue or withdraw a subject from the study for the following reasons at his/her discretion:

- Pregnancy
- Subject non-compliance with study requirements (e.g., study intervention non-compliance)
- If any clinical adverse event (AE), laboratory abnormality, or other medical condition or situation occurs such that continued participation in the study would not be in the best interest of the subject
- If the subject is no longer an appropriate candidate for participation
- There is evidence of progressive disease or unacceptable toxicity
- Subject unable to receive MSC injection, either due to subject choice or investigator decision based on MSC release guidelines

Subjects who sign the informed consent form but do not receive the the MSC injections will be replaced. Subjects who sign the informed consent form and receive the the MSC injections, then subsequently withdraw, or are withdrawn or discontinued from the study, will not be replaced.

The following actions will be taken if a subject withdraws, or fails to return for a required study visit:

- The site will attempt to contact the subject and reschedule the missed visit within 2 weeks and counsel the subject on the importance of maintaining the assigned visit schedule and ascertain if the subject wishes to and/or should continue in the study.
- Before a subject is deemed lost to follow-up, the investigator or designee will make every effort to regain contact with the subject where possible, 3 telephone calls and, if necessary, a certified letter to the subject's last known mailing address. These contact attempts shall be documented in the subject's study file.
- If the subject continues to be unreachable, they will be considered to be lost to follow-up.

If a subject is prematurely withdrawn from the study for any reason, the investigator will under all circumstances try to perform all evaluations described for the early termination visit

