9.0 STUDY TREATMENT

9.1 Description of the Investigational Medicinal Product (IMP)

Drug Substance:

Autologous bone marrow-derived MSCs at a concentration of 10×10^6 cells/mL

Drug Product (IMP):

Suspension of autologous bone marrow-derived MSCs suspended in a solution of Plasmalyte A containing 0.5% human serum albumin. Cells will be administered at one dose level, Dose 0, with a possible lower dose if the DLT criterion is reached. For each cell dosage we have set a 20% acceptable deviation. Dose levels and acceptable ranges (in parentheses) are as follows:

- Dose -1: $5 (4 - 6) \times 10^6$ MSCs (into one submandibular gland; to be used only if Dose level 0 is not tolerated)
- Dose 0: $10 (8 - 12) \times 10^6$ MSCs (into one submandibular gland)

If the MSC IMP is not administered to the patient due to a failure of the MSCs to expand to achieve the required dose/ or the MSC IMP does not pass QA testing, the subject will be withdrawn from study, and followed for 1 month post the aspiration procedure to ensure AE/SAEs are appropriately recorded. These subjects will be replaced in the study by the recruitment of another subject.

Route of administration: injection into one submandibular gland (must have 2 glands present). The gland selected will be the gland that received the lower radiation dose. The contralateral gland of each interested subject will be injected with autologous MSC IMP at Dose level 0 following completion of the primary objective with no DLTs reported.

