13.2 Determination of Sample Size

Patients in this pilot trial will undergo unilateral gland injection per FDA request. Associated 95% confidence intervals will be provided for the toxicity rate. To describe changes in quality of life or salivary function/composition between baseline and post-injection timepoints, separate one-way ANOVA models will be fit to the data for each measured outcome. After fitting the models to the data, comparisons between the timepoints will be calculated using Tukey's method. Due to the short time frame of intervention, we anticipate that adherence to the intervention will be high (>90% of patients will complete all mandatory study components) and that rates of follow-up will be similarly high (i.e., low rates of drop outs or lost to follow-up).

Interim analysis: In this pilot study, there is not a planned interim analysis.

Sample Size: Six to twelve patients will be accrued, depending on toxicity encountered. If 0/6 or 1/6 participants experience a DLT at Dose Level 0, sample size would be six. If 2/6 participants experience a DLT at Dose Level 0, another cohort would be enrolled at Dose Level -1. Sample size would then be up to 12 patients, unless 2 or more patients at Dose Level -1 experience a DLT, at which point the study would be stopped.

Length of follow-up: Patients are observed for DLT after MSC injection, with a follow-up of 4 weeks after injection. Secondary outcomes will be assessed at 24 months (end of study for patients). DLT is defined as: pain > 5 on a standard pain scale of 0-10 at 1-month after MSC injection OR any serious AE within one-month post-injection (probably or definitely caused by study treatment) or other toxicities described in section 9.7.

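### The per-protocol set is drawn from all enrolled subjects, so it can include subjects who were never injected and can exceed the treated set

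*Combined protocol and SAP*

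**What the plan says.** Section 13.3 describes the sets as "separate, hierarchically organized analysis sets as defined below". Three definitions then follow:

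- The first bullet reads "Intention to Treat (ITT) analysis set: The safety analysis set will consist of all patients enrolled". Despite the mismatched name inside it, its content is clear: everyone enrolled.
- The second bullet reads "Safety analysis set: The full analysis set will consist of all patients who received the injection of the IMP". Here too the names disagree, but the content is everyone injected.
- The third bullet reads "The per-protocol analysis set will consist of all patients of the ITT analysis set for whom no major protocol violations have been recorded". It names the ITT set as its parent.

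On use, the section says: "Efficacy parameters will be evaluated using the full analysis set, the per-protocol analysis set, and based on dose of IMP received". Baseline characteristics are summarised for all three sets (Sections 13.3 and 13.4).

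Two other sections foresee subjects who are enrolled and not injected. Under Section 9.1, if the cells do not reach the required dose or the product fails QA testing, "the subject will be withdrawn from study, and followed for 1 month post the aspiration procedure", and the subject is replaced. Section 8.7 lists among the reasons for withdrawal: "Subject unable to receive MSC injection, either due to subject choice or investigator decision based on MSC release guidelines".

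For analysis, Section 13.2 plans that "separate one-way ANOVA models will be fit to the data for each measured outcome", followed by Tukey comparisons between timepoints. Section 13.8 plans Wilcoxon signed-rank tests of change from baseline for patient-reported outcomes and salivary flow.

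**The concern.** A per-protocol set is meant to show outcome in subjects treated as planned. This definition has no treatment requirement, so it can admit subjects who received nothing. Such a subject has baseline saliva and quality-of-life values but no visit timed from an injection. In an unpaired comparison of timepoint means, that subject contributes to the baseline mean and to no follow-up mean. Part of the apparent change would then reflect who was measured at each time. The per-protocol N could also exceed the number treated, which is hard to explain in a report that calls its sets hierarchical.

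**Working it through.** The plan gives no figure to reproduce, so the check is one of set membership, followed by the size of any shift.

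**Membership**

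1. Enrollment is complete after consent, screening, confirmation of eligibility and registration (Section 10.2). Injection is not a condition.
2. Saliva and quality of life are collected at Baseline. That visit follows enrollment (Section 10.3) and is scheduled at day -42, against day -28 for aspiration and day 0 for injection (Section 10.1).
3. A product failure leads to withdrawal and replacement under Section 9.1. Section 12.4 defines a deviation as noncompliance. Following Section 9.1 is compliance, so no major violation need be recorded.
4. Section 13.8 assesses successful production of the product on an intent-to-treat basis, so production failures are meant to be in ITT.
5. Per-protocol is ITT minus major violators. The subject in step 3 is therefore in per-protocol but not in the injected set. With six injected and one such subject, the sets can number 7 and 6.

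**Which outputs are touched**

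| Output | Effect of a never-injected subject |
|---|---|
| Per-protocol N and baseline summaries | Included |
| One-way ANOVA/Tukey on per-protocol (13.2) | Enters the baseline mean only; no subject term is stated |
| Wilcoxon signed-rank (13.8) | None; the test needs both values |
| Full analysis set | None; injected subjects only |
| Analyses by dose received | None; no dose was received |

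**Size**

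Let n be the number injected, k the number never injected who remain in per-protocol, and d the gap between their mean baseline and that of the injected, in between-subject SDs. The baseline mean shifts by k × d/(n + k). Sections 3.1 and 13.2 give n = 6, or up to 12 if the lower dose level opens. The values of k and d are assumptions.

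| n | k | d = 0.5 | d = 1 |
|---|---|---|---|
| 6 | 1 | 0.5/7 = 0.07 | 1/7 = 0.14 |
| 6 | 2 | 1/8 = 0.13 | 2/8 = 0.25 |
| 12 | 1 | 0.5/13 = 0.04 | 1/13 = 0.08 |

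For scale, the standard error of a six-subject mean is 1/√6 = 0.41 SD, so a shift of 0.14 SD is about one third of it.

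**Illustration with assumed values**

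Take six injected subjects with baseline flows 0.10, 0.15, 0.20, 0.25, 0.30 and 0.35, each rising by 0.05. The baseline mean is 1.35/6 = 0.225, the follow-up mean is 0.275, and the change is 0.050. Add one never-injected subject with baseline 0. The baseline mean becomes 1.35/7 = 0.193, and the unpaired contrast becomes 0.275 − 0.193 = 0.082. If that subject's baseline is 0.50 instead, the baseline mean is 1.85/7 = 0.264 and the contrast falls to 0.011. The paired change stays at 0.050 in both cases, so the distortion can go either way.

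**The case against.** The best defence has four parts.

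- **Most efficacy output is safe.** The change-from-baseline tests that Section 13.8 names for flow and patient-reported outcomes are paired, and two of the three efficacy populations already exclude untreated subjects. This stands, and it sets the limits of the point. A reader might infer that the efficacy results in general are biased; the documents do not support that.
- **The text may be settled later.** Section 13.0 promises a formal SAP. Section 13.3 promises sort-out criteria before evaluation and set allocation before database lock. The word *major* is not defined, and a subject who declines injection might be classed as non-compliant. The claim of a hierarchy also suggests that nesting was intended. All of this leaves room for repair, but none of it changes the parent set that the text names, and the product-failure route does not depend on how refusals are classed.
- **There may be no such subject.** Section 5.5 reports that each patient's product was formulated for injection, and Section 7.1 speaks of the six subjects. Both point to a small k. Neither says how many were enrolled, so k = 0 is not shown. Nothing links product failure to baseline saliva, so a systematic gap d cannot be assumed either.
- **The ANOVA imbalance has another source.** An injected subject who later drops out also leaves baseline and follow-up means resting on different people, in any set. This stands: redefining the per-protocol set alone would not cure it.

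**Conclusion.** The definition is wrong as written. It admits never-injected subjects to an efficacy set and allows that set to exceed the injected set. The correction is minor. The set is supportive, all efficacy inference is declared exploratory (Sections 13.1 and 13.8), and the primary DLT endpoint does not depend on it.

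The possible distortion is k/(6+k) × d in the per-protocol baseline mean, or 0.07 to 0.14 SD for one such subject and d between 0.5 and 1. This rests on assumed k and d, on no major violation being recorded for the subject, and on an ANOVA fitted without a subject term. It would be too strong to say that the per-protocol baseline has in fact been shifted in this trial: the documents do not establish that any such subject exists.

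**What to change.** In Section 13.3, define the per-protocol set as all patients who received the IMP injection and have no major protocol violation. Base every change-from-baseline summary and timepoint comparison, including the Section 13.2 contrasts, on subjects with both a baseline and the relevant post-injection value. This second step also deals with imbalance from later dropout. Keep never-injected subjects in the ITT set for disposition and for the feasibility analysis of Section 13.8. While editing, align the names of the first two sets with their content.

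The cost is one sentence in Section 13.3 and one rule on paired values, both carried into the SAP that is to be written before database lock. No new data are needed.

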13.4 Demographics and Baseline Characteristics

Demographics (age, sex, racial, ethnic group based on standard NIH categories) and baseline characteristics will be summarized by means of descriptive statistics for continuous data or frequency tables for categorical data. Demographic data and other baseline characteristics will be analyzed for all three-analysis sets.

13.5 Treatment and Study Compliance

The intervention in this study is a one-time injection that involves a procedure performed by study personnel so that there is limited concern with adherence to the intervention. The primary endpoint is based upon short-term outcomes and thus study compliance is expected to be good. Patients will be called by study coordinator to remind them of all study visits. Secondary endpoints are assessed up to 24 months after the intervention. To maximize study compliance, patients will receive regular reminders of study visits and all visits will be scheduled up to 1 year in advance.

The number of patients who complete each study visit and assessment will be provided in a CONSORT diagram at the time of publication.

13.6 Handling of Missing Data

Guidelines promulgated in the National Research Council report on handling of missing data will be followed^{48,49}.

13.7 Analyses of the Primary Endpoints

The primary objective of the study is to evaluate the safety and tolerability of MSCs for subjects with xerostomia after radiation for HNC.

The primary endpoint is the recommended starting dose of MSCs for a Phase I dose-escalation study, which will be determined by the proportion of subjects experiencing DLT, where DLT is defined as:

pain > 5 on a standard 10-point pain scale of 0-10 at 1-month after MSC injection OR any serious AE OR any of the selected toxicities listed in section 9.7, within one-month post-injection.

Adverse events will be processed in the statistical analysis after classification into standardized medical terminology using the NCI Common Terminology Criteria for Adverse Events, Version 5.0 (CTCAE v5.0) grouped by grade/severity, attribution/relatedness and expectedness.

All adverse events data will be listed in the individual patient data listings, including all information documented on the adverse event form. Separate listings will be provided likewise for serious adverse events, adverse events in subjects who died, and for adverse events leading to discontinuation of the study. Concomitant medication documented in relation to the occurrence of a serious adverse event after MSC administration on SAE forms will be listed separately as 'Concomitant medication as documented on SAE forms after MSC administration'.

Frequency tabulations of the number and percentage of patients with a pain rating of less than 6 on a VAS of 0-10 will be presented and displayed graphically with two-sided 95% confidence intervals using the Wilson score method.

Standard descriptive summary statistics (i.e., n, arithmetic mean, standard deviation, median, lower/upper quartiles, and minimum/maximum values) will be calculated for continuous variables. Categorical data will be presented in frequency tables using counts and percentages. Graphical presentation will be given by means of box and whisker plots and bar charts, as appropriate.

13.8 Analyses of the Secondary Endpoints

Analyses of the secondary endpoints focus on efficacy of the IMP in the treatment of xerostomia and hyposalivation. All inferential analyses for the secondary outcome variables will be interpreted in the exploratory sense, only.

Patient-reported outcome measures will be evaluated by comparing the changes in salivary QOL from baseline to each follow-up visit and by assessing changes over time, within-group comparisons will be performed with the Wilcoxon signed-rank test.

Salivary flow rate analysis will be analyzed in a manner described by Gronhoj et al. 2018²⁴: by comparing the changes from baseline to each follow-up visit and changes over time, within-group comparisons will be performed with the Wilcoxon signed-rank test.

Salivary composition analyses will focus on qualitative aspects of saliva previously found to change following radiation treatment: salivary pH^{39,40}, total protein concentration (mg/mL)^{41,42}, amylase (mU/mL)^{39,43}, and mucins (MUC5B, mU/mL)^{43,44}. Given that MSCs will be injected into one of the submandibular glands which contain both serous and mucous acinar secretory cells, we will measure products of both types of cells (both= total protein and pH; serous= amylase; mucous= mucins). Salivary pH will be measured using a pH meter (Orion 9810BN, Thermo Scientific). Enzyme-linked immunosorbent assays (ELISAs) will be used to quantify total protein, amylase, and mucin levels. Saliva composition will be assessed on whole saliva samples collected from subjects at the screening visit and the in-person follow-up visits.

To assess the imaging characteristics of submandibular gland after MSC injection, salivary gland size will be measured by ultrasound⁴⁵. Ultrasound imaging is a non-ionizing, noninvasive imaging modality that can be quickly obtained in a standard exam room. Three-dimensional (3D) Bmode data sets will be acquired for tumor volume measurements. If post-RT submandibular glands suppress ultrasound waves to prevent the visualization of the lower outline of the gland, a 2D estimate of gland size will be made.

Standard descriptive summary statistics (i.e., n, arithmetic mean, standard deviation, median, lower/upper quartiles, and minimum/maximum values) will be calculated for continuous variables. Categorical data will be presented in frequency tables using counts and percentages. Graphical presentation will be given by means of box and whisker plots and bar charts, as appropriate.

Results from physical examinations will be summarized for each scheduled study visit by means of a frequency table.

Briefly, assessment of feasibility for a future Phase I dose-escalation study will be accomplished by analyzing the drop-out rate and reasons for drop-out, time from patient inclusion to administration of the IMP and successful production of MSC IMP on an intent to treat basis.

